## 3. METHODOLOGY:

- **Type of Study:** prospective observational study
- **Study Setting:** Ain Shams University and Watany Eye Hospital, Cairo, Egypt.
- **Study Period:** through study completion, an average of 2 years
- **Study Population**

### *- Inclusion Criteria:*

- Subjects aged 21 – 45 years from both sexes.

- myopia up to -8 D
- Corneal astigmatism up to -5 D.
- Stable refraction for 1 year before surgery.
- No ectasia.
- Corneal thickness of more than 500  $\mu\text{m}$ .
- Calculated residual stromal bed of more than 300  $\mu\text{m}$ .
- Axial length up to 30 mm.

- Exclusion Criteria:

None of the patients enrolled have:

- History of previous ocular surgery.
- History of previous ocular trauma.
- Corneal opacities within the central 7 mm.
- Moderate to severe dry eye diseases.
- Active or previous diseases linked to the anterior segment of the eye.
- Active or previous diseases linked to the posterior segment of the eye.
- Diabetic patients.
- Patients with collagen vascular diseases.
- Patients with glaucoma.
- Patients with post-operative complications

• **Sample Size** (100 eyes) will be divided equally into 2 groups:

- Group 1: subjects have anterior corneal astigmatism of -1.5 to -5 D.
- Group 2: subjects have anterior corneal astigmatism below -1.5 D.

• **Ethical Considerations**

The study will be conducted in accordance with the ethical standards stated by the ethical committee in the Faculty of Medicine- Ain Shams University,

with informed consent.

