#### • **Study Procedures**

All patients will be scanned by OCULUS Pentacam® HR, Germany and all of them will be subjected to topography-guided femto-Lasik using the FS200 (Alcon Wavelight, Erlangen, Germany) and EX500 devices (Alcon Wavelight, Erlangen, Germany). And all of them will be done by one surgeon.

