#### • **Study Interventions**

All of them will undergo a complete ophthalmic examination to include or exclude cases, examinations including uncorrected distance visual acuity (UDVA) and corrected distance visual acuity (CDVA), IOP measurement, slit lamp examination, fundus examination, and Pentacam tomography.

At least 5 Pentacam scans will be taken for every patient each time. All Pentacam images will be collected and analyzed to measure the horizontal angle kappa, anterior astigmatism and its axis, back elevation data at the thinnest point, Anterior chamber depth and Axial length.

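### An enrolment exclusion for post-operative complications most likely removes patients after the study LASIK, which opens the estimated effect to selection bias

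*Protocol*

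**What the plan says.** The Exclusion Criteria in section 3 (Methodology) of the protocol open with "None of the patients enrolled have", and the last item in the list is "Patients with post-operative complications". The item does not name the operation, define a complication or give a time window.

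Other parts of section 3 bear on its meaning:

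- Type of Study: the design is a "prospective observational study".
- Study Procedures: "all of them will be subjected to topography-guided femto-Lasik". This is the only operation the protocol describes.
- Study Interventions: eligibility is settled by examination, "All of them will undergo a complete ophthalmic examination to include or exclude cases".
- Inclusion Criteria: "Stable refraction for 1 year before surgery", where the operation meant is the study operation.
- Exclusion Criteria: earlier eye operations have their own item, "History of previous ocular surgery".

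Section 2 (Aim/Objectives) asks how treating astigmatism affects angle kappa and corneal back elevation. It does not limit the question to eyes without complications.

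**The concern.** An eligibility criterion should rest on facts known before treatment. If this item refers to the study operation, it depends on an event that follows treatment, so in practice it is a rule for dropping treated patients.

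The eyes analysed would then be a selected set. If complications are related to the change in angle kappa or back elevation, the mean change in the remaining eyes does not describe all treated eyes. A comparison of the two astigmatism groups is exposed in the same way if complications differ between the groups in frequency or in effect.

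Two features add to the exposure. Complications are undefined, and the time of judgement is not fixed, so nothing in the protocol prevents the decision from being made with the post-operative scan in view. A link with the outcomes is also conceivable from the protocol itself. Section 1 (Introduction) associates a large angle kappa with decentred ablation and under-correction. If such results counted as complications, the item would tend to remove eyes with a large angle kappa. That statement concerns the level of angle kappa rather than its change, so it makes a link plausible and does not prove one.

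**Working it through.** **Step 1: which operation is meant.** There are two main readings.

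- *Complications of the study LASIK.* This fits the use of plain 'surgery' for the study operation in the Inclusion Criteria, and the fact that no other operation is described. The item then cannot be assessed at the enrolment examination, because the operation has not yet happened.
- *Complications of earlier eye surgery.* Such patients are already excluded by the item on previous ocular surgery, so the item would add nothing.

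The first reading is the more plausible. It is not certain, because the list overlaps with itself elsewhere: corneal opacities and glaucoma are named beside general items on anterior and posterior segment disease.

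**Step 2: size of a possible bias.** The protocol states no figure on this point, so there is none to reproduce. Let *p* be the share of treated eyes removed and *d* the mean change in complicated eyes minus that in uncomplicated eyes. Then

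mean(all treated) = (1 − p) × mean(uncomplicated) + p × mean(complicated) = mean(uncomplicated) + p × d,

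so removing the complicated eyes shifts the estimated mean change by p × d in size.

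Inputs:

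- *p* = 1% to 10%: assumed.
- *d* = 0.5 to 2 SD: assumed.
- Scale of 4.7 µm: section 1 (Introduction), the SD of back elevation at the thinnest point in normal eyes. It is a between-eye SD and not an SD of change, so the µm column is only illustrative.

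| p | d (SD) | shift (SD) | shift × 4.7 µm |
|---|---|---|---|
| 0.01 | 0.5 | 0.005 | 0.0235 |
| 0.02 | 1 | 0.02 | 0.094 |
| 0.05 | 1 | 0.05 | 0.235 |
| 0.05 | 2 | 0.10 | 0.47 |
| 0.10 | 2 | 0.20 | 0.94 |

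If p = 0 or d = 0, the shift is zero. As a check with 100 eyes, take 10 complicated eyes at 9.4 µm (2 × 4.7) and 90 at 0. The mean of all eyes is 94/100 = 0.94 µm and the mean after removal is 0, a shift of 0.94 µm.

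The protocol gives no SD for angle kappa, so for that outcome only the SD column applies.

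**Step 3: the comparison of groups.** Suppose, as a further assumption, that Group 1 loses 2% to 10% of its eyes, Group 2 loses half that share, and *d* is the same in both. The shift in the group difference is (p − p/2) × d. The smallest case is 0.01 × 0.5 × 4.7 = 0.024 µm and the largest is 0.05 × 2 × 4.7 = 0.47 µm.

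**Step 4: scale.** With 50 eyes per group treated as independent, and an assumed two-sided 5% level and 80% power, the detectable difference is (1.96 + 0.84) × √(2/50) = 0.56 SD, or 2.63 µm on the same scale. For a mean change in 100 independent eyes it is (1.96 + 0.84)/√100 = 0.28 SD.

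**The case against.** The strongest reply is that restriction to uncomplicated eyes may be deliberate. The study is observational and asks how astigmatism and its treatment relate to angle kappa and back elevation, not how safe the operation is. The effect in uncomplicated eyes is a defensible target. That stands, but the objective does not state this target, and an enrolment criterion is not the place to set it.

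The reading is also an inference. Redundancy is weak evidence in a list that repeats itself. That stands too, and it is why the conclusion is held with medium confidence. On the other reading the item is redundant and misleading, so the line still needs rewording.

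The magnitude is wholly assumed. The upper end needs both extremes at once, and even 0.20 SD lies below the detectable differences in Step 4. This is correct and limits how serious the point can be called. The item also excludes patients while the arithmetic counts eyes: if both eyes of a patient are enrolled, one complication could remove an uncomplicated eye as well. Nor does the protocol say whether the 100 eyes are counted before or after removal.

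The sentence "All Pentacam images will be collected and analyzed" carries little weight either way. It introduces the measurements taken from the scans and does not define an analysis set.

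Finally, analysis sets and sensitivity analyses may be left to a statistical analysis plan. But the defect is a rule that the protocol states, and an analysis plan would not correct the enrolment wording.

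**Conclusion.** The concern holds. Read in the most plausible way, the item conditions membership of the study on an event after treatment, and the resulting estimate is open to selection bias. No bias is demonstrated. Its direction is unknown and its size cannot be derived from the protocol.

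Under the assumptions above, the shift in mean change lies between 0.005 and 0.20 SD, roughly 0.02 to 0.94 µm of back elevation on a borrowed scale. It is zero if complications are absent or unrelated to the outcomes, and small if they are rare. This should be fixed because the correction is cheap, although the likely effect on the results may be modest.

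**What to change.** Delete the item from the Exclusion Criteria. Keep all operated eyes in the main analysis, using every available post-operative scan, and report by group the eyes without a usable scan. Report complications by group, and show uncomplicated eyes as a sensitivity analysis.

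If the sponsor wants the effect in uncomplicated eyes only, section 2 should say so. Complications should then be defined in advance without reference to angle kappa or back elevation, and the removed eyes reported by group. If complications of earlier surgery were meant, reword the item to say that.

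The cost is one line of protocol wording, a few more eyes in the analysis, and some added reporting (complications, unusable scans and one sensitivity analysis). The downside is a possibly larger SD.

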## 2. AIM/ OBJECTIVES :

The exact relation between anterior corneal astigmatism and angle kappa is still not scientifically understood.

The objectives of this study are to study:

The effect of treating astigmatism on angle kappa and corneal back elevation.

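### Does counting the sample in eyes, with no number of patients and no one-eye or both-eyes rule, make the planned comparison unsound?

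*Protocol*

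**What the plan says.** The sample is set in eyes under the eligibility criteria in section 3 (Methodology): "100 eyes) will be divided equally into 2 groups", which gives 50 eyes per group. The two groups are then worded by person: "Group 1: subjects have anterior corneal astigmatism of -1.5 to -5 D" and "Group 2: subjects have anterior corneal astigmatism below -1.5 D". Eligibility opens with "Subjects aged 21 – 45 years from both sexes". Surgery is described for patients as a whole (Study Procedures: "all of them will be subjected to topography-guided femto-Lasik"), and so is imaging (Study Interventions: "At least 5 Pentacam scans will be taken for every patient each time").

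The objective in section 2 is "The effect of treating astigmatism on angle kappa and corneal back elevation". The Statistical Analysis entry names only the software, Excel and SPSS. It gives no test, model, significance level or power. The protocol does not say how many patients will supply the eyes, whether a patient may contribute both, or how an eye would be chosen if only one enters.

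**The concern.** The two eyes of one person tend to resemble each other, so 100 eyes need not carry the information of 100 independent units. With the total in eyes and the groups in subjects, a reader cannot tell how many independent units the study will have. A person with one eye on each side of the 1.5 D boundary also appears to belong to both groups.

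If both eyes entered and were treated as independent, standard errors would be wrong. With both eyes in the same group they would be too small and false positives would rise. With fellow eyes in different groups the between-group test would be conservative. The pooled pre-to-post change over all 100 eyes, which is one direct reading of the objective, would still look more precise than it is.

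**Working it through.** **The plan's own figure.** The total of 100 eyes cannot be reproduced, because the protocol gives no effect size, standard deviation, significance level, power or dropout. Only the equal split follows: 100 / 2 = 50 eyes per group.

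**Number of patients.** One eye each: 100 / 1 = 100. Both eyes each: 100 / 2 = 50. The range of 50 to 100 is therefore right.

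**Effect of ignoring the pairing.** Let f be the share of eyes that are in pairs and r the inter-eye correlation of the pre-to-post change. The documents give neither, so both are assumptions.

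- Same-group pairs, or the pooled change over all eyes: variance factor V = 1 + f × r.
- Between-group difference when all pairs are split across the groups: V = 1 − r.
- True level of a nominal two-sided 5% test: 2 × (1 − Φ(1.96 / √V)).
- Effective number of eyes for the V = 1 + f × r cases: 100 / V.

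| Setting | r | V | Effective n | True level |
|---|---|---|---|---|
| One eye per patient | any | 1.00 | 100 | 5.0% |
| All eyes in same-group pairs | 0 | 1.00 | 100 | 5.0% |
| | 0.1 | 1.10 | 90.9 | 6.2% |
| | 0.3 | 1.30 | 76.9 | 8.6% |
| | 0.5 | 1.50 | 66.7 | 11.0% |
| | 0.9 | 1.90 | 52.6 | 15.5% |
| Half the eyes in same-group pairs (75 patients) | 0.1 | 1.05 | 95.2 | 5.6% |
| | 0.3 | 1.15 | 87.0 | 6.8% |
| | 0.9 | 1.45 | 69.0 | 10.4% |
| All pairs split, between-group test | 0.3 | 0.70 | – | 1.9% |
| | 0.5 | 0.50 | – | 0.6% |
| | 0.9 | 0.10 | – | below 0.01% |

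With all pairs split, the pooled change has V = 1 + r, so its levels are those of the rows with all eyes in same-group pairs. Simulated t-tests, 20,000 per setting, agree closely. For all eyes in same-group pairs they gave 8.4%, 11.2% and 16.0% at r = 0.3, 0.5 and 0.9.

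**Precision.** Assuming a two-sided 5% level and 80% power, the detectable between-group difference is (1.96 + 0.84) × √(2 / n) standard deviations. This is 0.56 for n = 50 independent units per group and 0.79 for n = 25. The protocol makes no power claim that either value could contradict.

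**Units side by side.** The sentence that sets the sample divides eyes. The criteria listed under subjects include corneal astigmatism, corneal thickness, residual stromal bed and axial length, all of which are properties of an eye. The protocol thus uses the word for the person where it means the eye. Read that way, a person with eyes on both sides of the boundary contributes one eye to each group, and the apparent conflict goes away.

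**The case for a change.** The best case for a change is that enrolment belongs in the protocol. How many patients enter, which of their eyes, and in which group are not questions of modelling. An analysis plan can account for clustering afterwards, but it cannot restore an eye-selection rule that was never applied when patients were recruited. The remedy would be cheap: a sentence on the unit and the number of patients and, if both eyes enter, an analysis that clusters on the patient, which SPSS can do without extra measurements.

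Much of this stands. The omission is real, the range of 50 to 100 patients is correct, and the conditional error rates are correct. What does not follow is that the plan is wrong. Every inflated error rate needs two things that the protocol does not state: that both eyes enter, and that they are analysed as independent. Even the direction is open, because the between-group test could be too liberal, correct or too conservative, depending on where fellow eyes fall. A model for paired eyes would replace no method named in the protocol, and choosing one is ordinary content for an analysis plan.

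**Conclusion.** No change to the plan follows. The protocol leaves the number of patients and the eye rule unwritten and words its groups loosely, but it states no figure, test or rule that this makes wrong. An analyst would group each eye by its own astigmatism and, if both eyes of a patient are present, allow for the pairing.

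The consequence of not doing so runs from none (one eye per patient, or r = 0) to a true level of about 15.5% for a nominal 5% test (all eyes in same-group pairs, or the pooled change with all patients bilateral, at r = 0.9). With all pairs split, the between-group test has a level of 1.9% or less once r is 0.3 or more. These figures rest on assumed correlations and an assumed naive analysis. They do not show that 100 eyes is too few. Stating the number of patients and the eye rule would help readers, but as a clarification only.

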## 1. INTRODUCTION/ REVIEW

Astigmatism has a corneal component and a lenticular component. Corneal astigmatism occurs when there are differences in the radius of curvature of the cornea in different meridians. ([Morlet et al, 2002](#)).

Astigmatism is classified as “with the rule” when the steep meridian on the corneal surface is between 60 and 120 degrees, and as “against the rule” when the steep meridian on the corneal surface is between 0 and 30 degrees or between 150 and 180 degrees. As the dioptric power of the posterior corneal surface is negative, posterior corneal astigmatism is classified as “with the rule” when the steep meridian on the corneal surface is between 0 and 30 degrees or between 150 and 180 degrees, and as “against the rule” when the steep meridian on the corneal surface is between 60 and 120 degrees. ([Koch et al, 2013](#)).

The magnitude of corneal astigmatism has been reported to vary with age. ([Attebo et al, 1999](#)). There is a shift of the steepest corneal meridian from the vertical (with-the-rule) to the horizontal meridian (against-the-rule). ([Mohammadi et al, 2016](#)).

The mean percentage and magnitude of astigmatism in the population aged 15

to 65 years are:  $\geq 0.5$  diopter (D) in 73.53%,  $\geq 1.0$  D in 32.78%,  $\geq 1.5$  D in 13.55%,  $\geq 2.0$  D in 6.86% and  $\geq 3.0$  D in 2.47%. (Gabor et al, 2013)

Angle kappa represents the angle between the visual and pupillary axes (Park et al, 2012). The visual axis connects the fovea with the fixation point and passes by the nodal point. The pupillary axis is the line passing through the center of the pupil perpendicular to the cornea. Angle kappa can be classified as positive (nasal) or negative (temporal). A positive angle kappa of  $5.0^\circ$  on average is generally found in the normal human eye. (Yeo et al, 2012).

Angle kappa decreases with age and tends to be larger in emmetropes and hypermetropes than in myopes). (Hashemi et al, 2010). But the relation of astigmatism to angle kappa still needs further studies. (Larysa et al, 2021).

Angle kappa is a crucial parameter in some surgical decisions. In keratorefractive surgery with a large angle kappa, there is a greater chance of decentration of ablation zones, and it may lead to negative visual effects such as high-order aberrations and under-correction. (Harrer et al, 2017 )

Angle kappa is a crucial parameter for proper centration of multifocal intraocular lens implantation. (Prakash et al, 2011)

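### Eyes are grouped by size of astigmatism alone while angle kappa is measured only horizontally, so the contrast may be diluted and depends on an uncontrolled axis mix

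*Protocol*

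**What the plan says.** All references are to the protocol, section 3 (Methodology), unless stated.

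- **Grouping.** Under the inclusion and exclusion criteria, the sample of "100 eyes) will be divided equally into 2 groups" is split by size of anterior corneal astigmatism: "Group 1: subjects have anterior corneal astigmatism of -1.5 to -5 D" and "Group 2: subjects have anterior corneal astigmatism below -1.5 D". Neither the grouping nor eligibility has an axis condition.
- **Outcome and recorded data.** Study Interventions says the Pentacam images will be used "to measure the horizontal angle kappa, anterior astigmatism and its axis, back elevation data at the thinnest point". Kappa is therefore one directional component. The axis is collected, but no later text uses it.
- **Axis classes.** The Introduction calls anterior astigmatism with-the-rule "when the steep meridian on the corneal surface is between 60 and 120 degrees", and against-the-rule when that meridian is within 30 degrees of horizontal.
- **Sphere.** Eligibility also admits "myopia up to -8 D".
- **Objective.** Section 2 asks for the effect of treating astigmatism on angle kappa and on corneal back elevation.
- **Analysis.** The Statistical Analysis paragraph names only the software.

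**The concern.** Astigmatism has a size and a direction. The protocol pairs an exposure stripped of direction with an outcome taken in one direction. Two eyes with the same cylinder can have very different treatment along the horizontal meridian, and a Group 1 eye can have less than a Group 2 eye.

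If the effect on horizontal kappa depends on direction, comparing the groups mixes eyes in which it should be large with eyes in which it should be near zero. The result would then depend partly on how many with-the-rule and against-the-rule eyes happen to fall in each group. A weak or absent group difference could be read as no effect of astigmatism treatment. Replacing the two groups by size as a continuous variable does not remove the problem, because size still carries no direction.

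**Working it through.** The protocol gives no derivation for its 100 eyes and no figure on this point, so there is no stated number to reproduce.

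**1. Power removed along the horizontal.** For a cylinder of size C with steep meridian θ, full correction that flattens the steep meridian (an assumption) removes C cos²θ along the horizontal. cos² at 0, 30, 60 and 90 degrees is 1, 0.75, 0.25 and 0. On the Introduction's axis classes:

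- with-the-rule: 0% to 25% of C
- against-the-rule: 75% to 100% of C

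A 3 D with-the-rule eye (Group 1) therefore loses 0 to 0.75 D horizontally. A 1 D against-the-rule eye (Group 2) loses 0.75 to 1.0 D.

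**2. Sizes in each group.** The Introduction's prevalences are 73.53% at 0.5 D or more, 32.78% at 1.0, 13.55% at 1.5, 6.86% at 2.0 and 2.47% at 3.0. Sizes are assumed uniform within bands, with 5 D as the top.

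- Group 1 mean: (6.69×1.75 + 4.39×2.5 + 2.47×4)/13.55 = 2.40 D
- Group 2 mean: (26.47×0.25 + 40.75×0.75 + 19.23×1.25)/86.45 = 0.71 D

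**3. Axis mix.** The protocol gives none, so a range is assumed. Axes are uniform within each class, with oblique as 30–60 and 120–150 degrees. The average of cos²θ is then 0.0865 (with-the-rule), 0.9135 (against-the-rule) and 0.5 (oblique). For 60/20/20 the average fraction is 0.6×0.0865 + 0.2×0.9135 + 0.2×0.5 = 0.335, giving 2.40×0.335 = 0.80 D and 0.71×0.335 = 0.24 D. Wrong-order pairs and variance shares come from simulating 400,000 eyes per group.

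| Mix, with/against/oblique % (Group 1; Group 2) | Mean cylinder removed horizontally, D | Pairs in wrong order | Variance explained by group | Variance explained by continuous size |
|---|---|---|---|---|
| thirds; thirds | 1.20 vs 0.35 | 23% | 24% | 40% |
| 60/20/20; same | 0.80 vs 0.24 | 29% | 14% | 24% |
| 80/10/10; 60/20/20 | 0.51 vs 0.24 | 38% | 5.5% | 12% |
| 90/5/5; 50/30/20 | 0.36 vs 0.30 | 48% | 0.4% | 5% |

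With sizes uniform within each group and the same mix in both (from all with-the-rule to equal thirds), wrong-order pairs are 20% to 26%.

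**4. Do the means reverse?** Not in any row. Reversal needs Group 2's average horizontal fraction to exceed Group 1's by more than 2.40/0.71 = 3.4 times. In the last row it is 0.417/0.149 = 2.8 times.

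**5. Sphere.** Spherical correction removes power in every meridian. With sphere assumed uniform over 0 to 8 D, C cos²θ explains only 12%, 10%, 6% and 4% of total horizontal power removed in the four rows. With sphere assumed uniform over 2 to 6 D it explains 36%, 30%, 20% and 14%. In minus-cylinder form with axis α, let M = S + C/2 and J0 = −(C/2)cos 2α. Horizontal power is S + C sin²α = M + J0 exactly. For −3.00 × 180 that is −1.5 + 1.5 = 0 D; for −3.00 × 90 it is −1.5 − 1.5 = −3 D. Spherical equivalent and J0 together therefore carry all of it.

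**The case against.** **The link to kappa is not in the documents.** Every percentage above concerns power removed horizontally, not kappa. The Introduction describes the device's kappa as a distance between pupil center and first Purkinje image, and section 2 says the relation to astigmatism is not understood. This stands: the size of any dilution in kappa itself is unknown. It is also a reason not to discard direction in a study of that relation.

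**The analysis may be settled elsewhere.** A statistical analysis plan not at hand may use the axis, and the protocol spells out no between-group test; a before/after analysis needs no groups. This stands in part. The size-only split is nevertheless a choice written into the protocol, and an analysis that simply compares the two groups inherits it.

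**A reader might infer that the group effect could come out reversed.** The calculations do not support that. Wrong-order pairs show overlap between individual eyes, not reversed means. The 38% and 48% rows also rest on axis imbalances between groups that nothing in the protocol suggests.

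**A reader might infer that C cos²θ is the right exposure.** It is not sufficient alone, because it omits sphere.

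**A reader might infer that age confounds the contrast.** The Introduction says kappa falls with age and the steep meridian moves toward horizontal. That concerns levels. A within-eye change removes baseline kappa, and nothing says the change depends on age. Age is worth a covariate, no more.

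**A reader might extend the point to back elevation or to averaging repeat axes.** The mismatch is with a horizontal outcome, which back elevation at the thinnest point is not, and the protocol does not say that axes are averaged.

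**Conclusion.** The point holds in a limited form. The protocol groups by size only, measures kappa horizontally only, and assigns no use to the axis it records. If horizontal kappa responds to the direction of the correction, the size contrast is diluted and depends on the axis mix. With the same assumed mix in both groups, 23% to 29% of pairs are in the wrong order for horizontal cylinder removed; with assumed imbalance this rises to 48%. Group membership explains 24% of the variance in that quantity at best and 0.4% at worst, and the group means keep their order throughout.

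These figures assume full correction, the Introduction's population prevalences for the sizes, uniform sizes within bands and axes within classes, and the stated mixes. The effect on kappa cannot be sized from the protocol. The change is worth making because it costs almost nothing, not because the present plan is shown to give a wrong answer.

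**What to change.** Keep the two size groups for description. In the Sample Size and Statistical Analysis paragraphs, add that the effect of astigmatism treatment on change in horizontal angle kappa will be estimated by regression on the change in J0 and J45 from before to after surgery. Both are computed from the recorded size and axis: J0 = −(C/2)cos 2α and J45 = −(C/2)sin 2α. Include change in spherical equivalent and age as covariates. The treated sphere could stand in for spherical equivalent, but the exact identity for horizontal power holds with spherical equivalent. Do not use C cos²θ as the only regressor.

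The cost is two derived variables, a few more model terms with 100 eyes, and a sentence or two of text. No new measurement, visit or patient is needed.
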